### 5.2 REPORTING PROCEDURES

All adverse events should be reported. Depending on the nature of the event the reporting procedures below should be followed. Any questions concerning adverse event reporting should be directed to the Chief Investigator in the first instance.

#### 5.3.1 Non serious AEs

All such events, whether expected or not, should be recorded.

#### 5.3.2 Serious AEs

An SAE form should be completed and emailed to the chief investigator within 24 hours. However, relapse and death due to other pathology, and hospitalisations for elective treatment of a pre-existing condition do not need reporting as SAEs.

All SAEs should be reported to the Chelsea Research and Ethics Committee where in the opinion of the Chief Investigator, the event was:

- ‘related’, i.e. resulted from the administration of any of the research procedures; and,
- ‘unexpected’, i.e. an event that is not listed in the protocol as an expected occurrence.

Reports of related and unexpected SAEs should be submitted within 15 days of the Chief Investigator becoming aware of the event, using the NRES SAE form for non-IMP studies. The Chief Investigator must also notify the Sponsor of all related and unexpected SAEs.

Local investigators should report any SAEs as required by their Local Research Ethics Committee, Sponsor and/or Research & Development Office.

**Please send SAE forms to: [[contact]](mailto:[contact])**

**[contact] (Mon to Fri 09.00 – 17.00)**

## 6.0 ASSESSMENT AND FOLLOW-UP

Follow up appointments at 3 and 6 months post -surgery will be carried out at the participants' respective hospital gynecology clinic responsible for the care and management of the ovarian cyst. During this appointment, the responsible physician will assess recovery post- surgery and perform a clinical assessment. A blood test to measure ovarian reserve including assessment of AMH will be taken by the outpatient gynaecology nurse or research staff assigned to the clinic. A transvaginal ultrasound scan will be performed during the appointment by an experienced gynaecology specialist trainee or Consultant to assess the AFC and preserved ovarian volume of tissue remaining. Any incidental findings identified on ultrasound scan of gynaecological pathology, will be managed by the responsible clinician and the participants GP will be informed by letter.

The majority of participants are likely to be discharged following the 2nd clinic appointment 6 months post- surgery, whereby no further involvement is required in the study. If a participant becomes pregnant during the follow up period, follow up will be deferred to 3 and 6 months post completion of pregnancy.

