**DESIGN**

A multi-centre prospective cohort non-blinded randomised controlled trial

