## 3.0 STUDY DESIGN

This will be a multi-centre prospective cohort study carried out as a non-blinded randomised controlled trial. Participants will be allocated to either a control group of laparoscopic ovarian cystectomy performed without ultrasound guidance, or to the experimental ultrasound guided laparoscopic ovarian cystectomy (UGLOC) group. All surgeons operating and participants recruited to the study will be aware of which group they have been allocated to from the beginning of the study. The investigators aim for equal sample sizes in both groups (see power calculation below).

Participants will include all women of reproductive age diagnosed with a benign ovarian cyst requiring surgical management. The duration of the study from recruitment to end of data collection will be approximately 3 years (01/10/21-01/10/24).

Women referred to the outpatient gynecology clinic with a suspected ovarian cyst will be asked about their clinical history and undergo a pelvic transvaginal ultrasound scan (2D and 3D ultrasonography) as part of routine clinical care. If an ovarian cyst is seen on ultrasound, it will be assessed according to local protocols based on simple descriptors and international ovarian tumor analysis (IOTA) simple rules. Depending on the severity of symptoms, nature of the cyst and fulfilment of the inclusion criteria and if the woman is suitable for surgical management, she will then be invited to participate in the study.

Participants will be recruited from various general gynaecology clinics as well as specialist clinics including: ovarian cyst, the IOTA and rapid access clinics across Imperial and University College London Hospital.

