### *Surgical Intervention*

The same surgeons will operate on participants in both the control and experimental group. This will aim to exclude bias which may otherwise attribute findings to the surgeon operating. Surgery will be performed at Imperial Healthcare NHS Trusts and at the University College London Hospitals NHS Foundation Trust by an experienced clinician.

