### *Data Collection*

The investigators will collect the following data: patient demographics including age, BMI, gravida, parity and gynaecological surgical history. Pre-operative data will include findings from the diagnostic transvaginal scan and measure of ovarian reserve: AMH and AFC. Intra-operative data will include transvaginal findings during surgery (in the experimental group only), such as cyst location and size or any new lesions noted. Residual ovarian volume post cystectomy will also be measured intraoperatively. Histology data will include the histological diagnosis of the ovarian cyst and volume of normal ovarian tissue excised during the cystectomy measured as per margins in mm. Outcomes following surgery including duration of surgery (mins), length of hospital stay (days) and post op complications will be recorded.

Post operatively, participants will return to clinic for follow up at 3 and 6 months post -surgery, whereby a blood test will be taken to assess ovarian reserve by measuring the AMH level. The outpatient gynaecology nurse in clinic or research staff will be responsible for taking the blood sample

and will only require one EDTA bottle (yellow top) to be filled (20-40mls). The blood samples will be processed by Imperial College Healthcare Trust laboratories or University College London Hospitals NHS Foundation Trust, depending on the site taken, and will be discarded as per local protocol once the AMH has been determined. There are no specific storage or transfer requirements outside of normal practice. Therefore, samples will be ‘podded’ to the labs once taken in the usual way. In addition, an ultrasound will be performed during the follow up appointment to measure AFC and assess volume of preserved ovarian tissue. Follow up appointments should take approximately 20 minutes. The two blood tests and two ultrasound scans carried out during the follow up process are considered standard clinical practice, and therefore not considered additional investigations for the purpose of this research study.

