### 3.1 STUDY OUTCOME MEASURES

Primary: AMH and AFC measurements at 3 and 6 months post-surgery.

Secondary: Surgical outcomes including:

- Duration of surgical procedure (minutes),
- Duration of hospital stay (days)
- Presence of intra-operative cyst rupture or spillage (Yes/No)

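### The reader of the antral follicle count is fixed only by grade and experience, so a surgeon or intra-operative scanner who knows the allocation may count one of the two listed primary measures

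*SAP*

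**What the plan says.** Section 3.1 of the SAP defines the primary outcome as "Primary: AMH and AFC measurements at 3 and 6 months post-surgery". The design entry in the Study Summary reads "A multi-centre prospective cohort non-blinded randomised controlled trial", and section 3.0 adds: "All surgeons operating and participants recruited to the study will be aware of which group they have been allocated to".

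Section 6.0 places follow-up at each participant's "respective hospital gynecology clinic responsible for the care and management of the ovarian cyst". At that visit "the responsible physician will assess recovery post- surgery and perform a clinical assessment". A separate sentence has the transvaginal scan performed "by an experienced gynaecology specialist trainee or Consultant to assess the AFC" and the remaining ovarian volume. Grade and experience are the only conditions on the scan operator.

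Two other parts of section 3.0 bear on this. Under Data Collection, the intra-operative data include "transvaginal findings during surgery (in the experimental group only"), and AMH is obtained from a blood sample processed in the trusts' laboratories. Under Surgical Intervention, "The same surgeons will operate on participants in both the control and experimental group", a step the SAP takes to limit surgeon-related bias.

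**The concern.** AMH comes from a laboratory, whereas AFC is a number that the person holding the probe arrives at. Section 6.0 specifies who that person is, and the specification admits the readers with the closest interest in the result: the surgeon who used the technique and the clinician who guided it.

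There are two ways for error to enter. A reader who knows the arm may count more or fewer follicles according to what they expect. Also, intra-operative scanning takes place in one arm only, so someone who scanned in theatre and later follows up the same women would read mostly that arm. A personal tendency to count high or low would then look like a treatment effect. Having the same surgeons in both arms does not prevent the first of these, because a surgeon who reads the scan still knows each woman's group.

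The SAP guards against bias at allocation, with numbered sealed envelopes prepared by a separate group, and at surgery. It has no counterpart when AFC is read. At stake is whether an AFC difference, in either direction, can be attributed to the technique.

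**Working it through.** **1. What the text permits.** Setting section 6.0 beside section 3.0:

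- Surgeons know the allocation (3.0). Section 6.0 does not exclude them from scanning.
- Intra-operative scanners know the allocation, since they scan in the experimental arm only (Data Collection). Section 6.0 does not exclude them either.
- No reading of stored images, second reader or agreement check is described.
- The scan is live, at a visit that also reviews surgical recovery, with a woman who knows her group.

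The plan, followed as written, therefore allows a non-independent AFC reading. It does not require one.

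**2. The plan's own sample size, to see whether AFC enters it.** Inputs from section 7.0, Table 2: AMH means 17.06 and 3.57, SDs 22.28 and 4.31, 5% level, power 0.95, t-test on the log scale.

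- Log SD = sqrt(ln(1 + (SD/mean)²)) = 0.998 and 0.948; pooled 0.973.
- Log mean = ln(mean) − (log SD)²/2; difference between arms = 1.516.
- n per arm = 2 × (1.960 + 1.645)² × 0.973² / 1.516² = 10.7, rounded up to 11.

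This matches the stated minimum of 11. Adding the margin of 2 gives 13, and adding 3 for attrition gives 16. AFC appears nowhere in the calculation, so changing who reads AFC leaves both N and the AMH power as they are.

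**3. Illustration of what a reader shift would do.** The SAP gives no AFC SD and no estimate of reader bias, so the shift is an assumption, expressed in SD units. Suppose there is no true AFC difference and readings in one arm are shifted by b SD. A two-sided 5% t-test with n per arm then rejects with the probability given by a noncentral t distribution with 2n − 2 degrees of freedom and noncentrality b × sqrt(n/2). For n = 13, sqrt(13/2) = 2.55; for n = 16, sqrt(16/2) = 2.83.

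| Assumed shift b (SD) | Noncentrality, n = 13 | False-positive rate, n = 13 | False-positive rate, n = 16 |
|---|---|---|---|
| 0 | 0 | 5.0% | 5.0% |
| 0.1 | 0.25 | 5.7% | 5.9% |
| 0.2 | 0.51 | 7.8% | 8.5% |
| 0.3 | 0.76 | 11.4% | 13.0% |
| 0.5 | 1.27 | 23.2% | 27.8% |

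To translate the shift into follicles: if the SD were 5 (again an assumption), 0.2 SD would be one follicle. For a fixed shift the rate rises with n, so recruiting more women does not cure the problem. A shift against the experimental arm would instead hide a real benefit.

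Section 7.0 names the t-test for log AMH and the Wilcoxon rank sum test for comparing continuous variables in two groups. The t-test stands in here for whichever test is applied to AFC.

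**The case against.** The best reply is that the SAP is silent rather than wrong. Stating the grade of the scan operator is not an error, no sentence puts the surgeon at the probe, and the trial openly declares itself non-blinded. The first part has weight, and it rules out some inferences a reader might draw:

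- *That treating clinicians or surgeons do the scan.* Section 6.0 gives the clinical assessment to the responsible physician and the scan, in its own sentence, to a trainee or consultant. They may or may not be the same person.
- *That independent reading certainly needs no extra staff.* Eligibility is wide and two trusts take part, which makes it plausible. But the SAP gives no number of eligible scanners and no rotas, and section 8.6 says that the study does not require specific funding.
- *That half of the trial's evidence is compromised.* AFC is one of two listed measures, but the sample size and the named test rest on AMH, which no reader can shift and which is measured at the same visits.
- *That an uninvolved reader would be blind.* The woman knows her group and can reveal it during a live scan.
- *That the inflation is known.* The size and direction of any shift are assumed, and a small shift such as 0.1 SD does little.

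What does not stand is the appeal to the open design. Surgeons cannot be masked to their own operation, but that does not stop a different clinician counting follicles three or six months later. Nor is this mere silence: the SAP does specify the reader, and the specification lets in someone who delivered the technique.

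**Conclusion.** The point holds in a limited form. As written, section 6.0 allows an operator-read primary measure to be counted by someone who knows the allocation and may have performed or guided the surgery. That exposes the AFC comparison to assessment bias. AMH, its power and the 16 per arm are unaffected.

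The size and direction of the bias cannot be derived from the document. The range of about 6% to 23% should be read only as an illustration: it assumes a reader shift of 0.1 to 0.5 SD, 13 evaluable women per arm, a t-test and no true difference. The document does not show that such a shift will occur, or that the surgeon will be the reader. The change is a cheap improvement to the AFC result, not a repair without which the trial fails.

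**What to change.** In section 6.0, state that:

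- wherever the existing clinic rota allows, AFC at 3 and 6 months is counted by an eligible trainee or consultant who took no part in that woman's surgery or intra-operative scan;
- the reader records the count before seeing the operation note or the allocation;
- the woman is asked not to disclose her group before the count is recorded;
- the case report form records who read the scan and whether they knew the allocation.

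In section 7.0, keep every scan in the main AFC analysis and add a sensitivity analysis that leaves out the non-independent reads. Interpret it with caution: with about 13 women per arm it loses precision, and if non-independent reads are commoner in one arm or at one site it may unbalance the comparison.

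The cost is a rota constraint that may not always be met, one addition to the case report form and one extra analysis. N and the visit schedule do not change. Masking will be only partial, but the recorded field will show how far it held.

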## 7.0 STATISTICS AND DATA ANALYSIS

A study by Kwon et al investigated the impact of laparoscopic ovarian cystectomy for benign cysts on post-operative ovarian reserve, as measured by follow up AMH levels taken 3 months after surgery. This particular study is considered to be most applicable for determining the power calculation of our proposed randomised controlled trial based on the following principles: pathology of the ovarian cysts were benign in nature and the sample size of the paper is one of the largest reported in the literature review.

From a sample size of 100 women, this paper deduced that AMH levels decreased on average 30.58% (+/-29.66%) between the pre-operative value to the level assessed 3 months following surgery. Specifically, the group of participants who underwent laparoscopic ovarian cystectomy for benign ovarian pathology had a mean (+/-SD) serum AMH of 1.59 (+/- 1.92)(ng/ml), which when converted to (pmol/L) is 3.57 (+/-4.31).

At present there are no reported studies assessing the change in AMH levels following ultrasound guided ovarian cystectomy. However, the investigators of this study have performed a small number of ultrasound-guided surgeries on 5 women, and therefore have a small data set, which can be considered a *pilot* study.

Amongst 5 women who have undergone ultrasound guided laparoscopic ovarian cystectomy, the mean difference (+/-SD) in AMH levels measured 3 months post operatively from pre-op levels is: 14.46 (+/- 21.02) pmol/L. This represents a substantial clinical difference according to previous research, and would imply women being less likely to experience fertility issues as they would be near the lower end of the normal range of AMH rather than in the lowest decile (ca. 0-4.5).

In order to calculate the sample size, the investigators have leveraged the pilot data to derive an estimate of the mean and standard deviation. From the literature, it can be assumed AMH is approximately log-normally distributed, as demonstrated from figure 1. Using this figure, the investigators have determined the normed (percentile) transformation of values from the pilot study.

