**(Table 1)**

Figure 1: Normed percentile transformation of AMH Values

[figure not shown]

Table 1: Estimated values of AMH differences based on normed percentile transformation

AMH Differences (pmol/L)		
	Treatment Group	Control Group
Mean	17.06	3.57
Standard Deviation (SD)	22.28	4.31
Coefficient of variation (CV) =(SD/Mean)	1.31	1.21
Number of participants	5	100

Using the pilot data, the investigators anticipate that 32 participants will be required to demonstrate a differential AMH level. (**Table 2**)

Table 2: Power Calculation

Sample Size Calculation		
	Treatment Group	Control Group
Mean (pilot)	17.06	3.57
Standard Deviation SD (pilot)	22.28	4.31
Standard Error (S.E)	6.18	1.08
Lower CI	4.70	1.42
Upper CI	29.42	5.73
Minimum (n)	11	11
Small sample margin	2	2
Attrition (assumed)	3	3
Total (n)	16	16

The minimum sample size is 11 participants. Considering the small size of the pilot and the very low risks thus far, the investigators include 2 more observations to boost power, and assume an attrition rate of approximately 25%. This leads to a total (n) of 16 participants per arm, with a power of 0.95 to detect a difference at the 5% level using a standard t-test on the log-transformed difference in means of AMH, the robust proxy for fertility. It will be necessary to perform an interim analysis given the low number of participants available for the power calculation.

With regards to further data analysis of the study, the investigators plan to use descriptive statistics (mean +/- standard deviation), two-sided tests, and Wilcoxon rank sum test to compare continuous variables in two groups. For more than two groups, the Kruskal-Wallis exact test will be used. For comparing a proportion with an expected value, a binomial exact test will be used. Results are considered significant at  $p<0.05$ . Analysis will be performed with SAS (version 9.2) and Statistical Package for Social Sciences for Windows (version 16). Statistical analysis will be performed under the supervision of [name].

Data and all appropriate documentation will be stored for a minimum of 10 years after the completion of the study, including the follow-up period.

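### The control AMH is converted to pmol/L with a factor of 2.245, about a third of the factor that AMH's molar mass implies, and this produces most of the planned effect

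*SAP*

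**What the plan says.** SAP section 7.0 builds the power calculation on two sources. The control arm comes from a published cohort of 100 women having laparoscopic cystectomy, with "serum AMH of 1.59 (+/- 1.92)(ng/ml), which when converted to (pmol/L) is 3.57 (+/-4.31"). The experimental arm comes from the investigators' own five ultrasound-guided cases, given directly in pmol/L: the change "measured 3 months post operatively from pre-op levels is: 14.46 (+/- 21.02) pmol/L".

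The section then says that "it can be assumed AMH is approximately log-normally distributed" and describes a percentile transformation of the pilot values, which become 17.06 (SD 22.28). The control values go into Tables 1 and 2 untransformed. Table 2 reads "Mean (pilot) 17.06 3.57" and "Standard Deviation SD (pilot) 22.28 4.31" (treatment, then control).

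From these inputs the plan obtains a minimum of 11 per arm. It adds 2 as a margin and 3 for attrition, reaches 16 per arm, and states that "the investigators anticipate that 32 participants will be required to demonstrate a differential AMH level". Power is given as 0.95 at the 5% level, "using a standard t-test on the log-transformed difference in means of AMH". The clinical argument is that women in the experimental arm would be "near the lower end of the normal range of AMH rather than in the lowest decile (ca. 0-4.5").

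**The concern.** Converting a mass concentration to a molar one leaves a single free quantity, the molar mass. The factor behind the control figures does not fit AMH, and the SAP neither states nor explains it. Since the pilot figures are already in pmol/L, a conversion that is too small affects one arm only and widens the gap between arms.

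Three things depend on the control mean of 3.57: the planned difference of 17.06 − 3.57 = 13.49 pmol/L, the minimum of 11 per arm, and the placing of control women in the lowest decile. If the control mean is about three times larger, the stated 0.95 power for the AMH primary outcome is lost.

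**Working it through.** **Inputs (SAP section 7.0, Tables 1 and 2).** Control 1.59 (SD 1.92) ng/ml, shown as 3.57 (4.31) pmol/L. Treatment 17.06 (22.28) pmol/L. Log-normal AMH, t-test on the log scale, two-sided 5%, power 0.95.

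**Step 1: the factor used.** 3.57/1.59 = 2.2453 and 4.31/1.92 = 2.2448, so one multiplier of 2.245 was applied to both. Since 1 ng/ml = 10⁶/M pmol/L, with M in g/mol, M = 10⁶/2.245 ≈ 445,000 g/mol.

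**Step 2: the factor for AMH.** Assumption, not in the SAP: M ≈ 140,000 g/mol, so the factor is 10⁶/140,000 = 7.14. The factor used is 2.245/7.14 = 0.314 of this, about a third.

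**Step 3: reproduce the plan's 11 per arm.**
- Log SD = √ln(1 + CV²): 0.998 for treatment and 0.948 for control; root mean square 0.973.
- Log difference: ln(17.06/3.57) = 1.564 from the arithmetic means. Allowing for the log-normal mean-to-median correction, 1.564 − (0.998² − 0.948²)/2 ≈ 1.516.
- n = 2 × [(1.960 + 1.645) × 0.973/δ]² = 10.1 (δ = 1.564) or 10.7 (δ = 1.516). Both round up to **11**, the plan's figure. The exact t-test gives 11.1 to 11.8, that is 12.

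**Step 4: change only the factor, to 7.14.**
- Control mean 1.59 × 7.14 = 11.35; SD 1.92 × 7.14 = 13.71. The CV and log SD do not change, so the whole effect runs through the mean.
- Ratio of means: 17.06/3.57 = 4.78 becomes 17.06/11.35 = 1.50.
- Log difference: ln(17.06/11.35) = 0.407, or 0.359 with the mean-to-median correction. Standardised effect: 0.407/0.973 = 0.418, or 0.369.
- Exact two-sample t-test: **150 to 192 per arm** for 0.95 power. Power is 0.15 to 0.18 at 13 per arm (after attrition) and **0.17 to 0.21** at 16 per arm.

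**Step 5: share of the planned effect due to the conversion.** Raw scale: (11.35 − 3.57)/13.49 = 7.78/13.49 = 58%. Log scale: 1 − 0.407/1.564 = 74%, or 1 − 0.359/1.516 = 76%.

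**Step 6: sensitivity to the factor** (exact t-test; each range covers the two versions of the log difference).

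| Factor | Control mean, pmol/L | n per arm for 0.95 | Power at 13 per arm |
|---|---|---|---|
| 4 | 6.36 | 27–29 | 0.66–0.70 |
| 5 | 7.95 | 44–50 | 0.44–0.48 |
| 6 | 9.54 | 74–88 | 0.27–0.31 |
| 7 | 11.13 | 136–173 | 0.16–0.19 |
| 7.14 | 11.35 | 150–192 | 0.15–0.18 |
| 8 | 12.72 | 287–410 | 0.09–0.11 |

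**Step 7: the decile argument.** A control mean below 4.5 needs a factor below 4.5/1.59 = 2.83, if the decile limits are in pmol/L. At 7.14 the control mean is 11.35/4.5 ≈ 2.5 times that limit.

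**The case against.** The strongest reply is that the SAP does not contradict itself here. It prints no factor, molar mass or assay, so 2.245 is wrong only against an outside value. That is true, but the outside value is a unit constant rather than a study result, and the conclusion does not need exactly 7.14: every factor from 4 upwards misses the stated power. The percentile transformation cannot explain 3.57 either. The figure is presented as a unit conversion, and the transformation is described only for the pilot values.

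A second reply has more force. The pilot figure is described as a change from before surgery and the control figure as a serum level, so the two are not like for like. The 150 to 192 per arm therefore shows how far the plan's own calculation moves when one input is corrected. It is not the number this trial truly needs. That limit stands, but it does not rescue the conversion, which would remain wrong after the mismatch was repaired.

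Third, the statement that the conversion makes up most of the effect depends on factor and scale. At a factor of 5 the share is 32% on the raw scale and about 51% to 53% on the log scale. At 7 or above it exceeds half on both scales. The decile limits carry no printed unit, so the 2.83 threshold assumes pmol/L.

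The plan admits its thin basis and foresees an interim analysis, but it gives no rule for re-estimating the sample size, so that step does not correct the error.

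**Conclusion.** The conversion is wrong as written. The multiplier of 2.245 follows from the SAP's own figures; that it is about a third of the right value rests on the assumed molar mass of about 140 kDa. At 7.14 the conversion accounts for 58% of the planned raw difference and about three quarters of the log difference, which is the scale the plan tests on. With all other planning inputs held, the sample size for 0.95 power is about 14 to 17 times the stated minimum (150/11 to 192/11), and 16 per arm has power near 0.2. The lowest-decile rationale falls with it. The stated power and the total of 32 participants cannot stand on this calculation.

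**What to change.** State the conversion factor and its basis in section 7.0. Re-convert the control to about 11.4 (SD 13.7) pmol/L, and correct the control columns of Tables 1 and 2, including the standard error and confidence limits. Delete the contrast with the lowest decile. Restate the power that 16 per arm provides, with a range over plausible factors.

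Alternatively, base the calculation on the percentage decline in AMH that section 7.0 already cites (30.58%, SD 29.66%), which needs no conversion. The SAP prints no percentage change for the pilot, so the investigators would have to derive one from the five women's pre-operative and 3-month values. This route would also put both arms on the same kind of quantity.

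The correction costs a few numbers and one sentence, and changes no study procedure. Its consequence is larger: with power restated at about 0.2, the sponsor must justify 16 per arm on other grounds or revise the sample size.

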### 4.2 INCLUSION CRITERIA

All females of reproductive age with a diagnosis of a benign ovarian cyst requiring surgical management.

This includes cysts defined as dermoid, teratoma, simple cyst, functional, serous cystadenoma or mucinous cystadenoma from the initial diagnostic ultrasound.

A strict criterion for the US diagnostic features will include the following:

- Cyst size  $\geq 3\text{cm}$ ;  $\leq 10\text{cm}$
- International Ovarian Tumour Analysis Benign features (IOTA B):
  - Unilocular
  - Solid components: largest diameter  $\leq 7\text{mm}$
  - Acoustic shadows
  - No blood flow
  - Smooth multilocular cyst: largest diameter  $\leq 10\text{cm}$

Specifically:

- Pregnant participants can be included but will be analysed separately
- For participants selected for surgery, delay of surgery is not an exclusion criterion for this study, but for selected objectives we will use only those participants in whom surgery was performed within 180 days after the ultrasound examination
- With regards to age, participants can be selected only if 18-50 years old
- Participants whom only underwent transabdominal scanning can be included in the study, but will be analysed separately

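### The stated power of 0.95 compares a pre-to-post AMH difference in the pilot with a serum AMH level in the control cohort, after transforming only the pilot values

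*SAP*

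**What the plan says.** All of this is in SAP section 7.0, including Tables 1 and 2.

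- **Pilot (treatment) input, 5 women:** "the mean difference (+/-SD) in AMH levels measured 3 months post operatively from pre-op levels is: 14.46 (+/- 21.02) pmol/L". No sign is given. The next sentence says that "they would be near the lower end of the normal range of AMH rather than in the lowest decile (ca. 0-4.5" pmol/L, which describes a level.
- **Control input, cited cohort of 100 women:** the benign-cyst group "had a mean (+/-SD) serum AMH of 1.59 (+/- 1.92)(ng/ml"), converted to 3.57 (SD 4.31) pmol/L. The plan does not say whether this is pre- or post-operative.
- **Change in the cited cohort, reported separately:** "AMH levels decreased on average 30.58% (+/-29.66"%) from before surgery to 3 months after. This figure does not enter the calculation.
- **Transformation:** "the investigators have determined the normed (percentile) transformation of values from the pilot study". In Table 1 the pilot figures become 17.06 (22.28). The control figures stay at 3.57 (4.31). The title covers both columns: "Estimated values of AMH differences based on normed percentile transformation".
- **Result:** Table 2 gives a minimum of 11 per arm, plus 2 as a margin and 3 for attrition, making 16 per arm, "with a power of 0.95 to detect a difference at the 5% level using a standard t-test on the log-transformed difference in means".

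**The concern.** A power figure means something only if the two means are the same quantity measured in the same way. Here one is described as a within-woman change and the other as a concentration, and only one has been through a percentile transformation that raised it. The ratio 17.06/3.57 = 4.78 is then not an effect of ultrasound guidance on any single outcome. With no sign on the pilot difference, the text does not even show which direction counts as benefit.

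This calculation is the only justification for 32 participants. If the trial finds no difference, readers will take the result as 95%-powered evidence against benefit.

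**Working it through.** Power below uses the noncentral t distribution, two-sided 5%, equal arms. For a log-normal variable, log SD = √ln(1 + CV²) and log mean = ln(mean) − (log SD)²/2. The evaluable number per arm is 16 × 0.75 = 12 from the stated attrition rate, or 11 + 2 = 13 from Table 2's rows.

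**1. The plan's own figure.** The CVs are 22.28/17.06 = 1.31 and 4.31/3.57 = 1.21. The log SDs are 0.998 and 0.948, root-mean-square 0.973.
- Log ratio of means: ln(17.06/3.57) = 1.564; d = 1.564/0.973 = 1.607; power 0.948 at 11 per arm.
- Difference of log-means: 1.516; d = 1.558; power 0.935 at 11.

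A normal approximation gives n = 11, and the exact t calculation gives 12. The plan's arithmetic therefore reproduces, and 0.95 comes from this pair of inputs.

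**2. Can both be differences?** A 30.58% change on 3.57 is 3.57 × 0.3058 = 1.09 pmol/L if 3.57 is pre-operative, or 3.57/(1 − 0.3058) − 3.57 = 1.57 if post-operative. Neither is 3.57, and the text calls 3.57 a serum AMH.

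**3. Can both be levels?** That contradicts the definition of the pilot figure and still leaves the one-arm transformation. Undoing it with 14.46 (21.02), CV 1.454, gives log SDs of 1.066 and 0.948, root-mean-square 1.009.

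| Effect measure | d | Power at 11 / 12 / 13 / 16 per arm | n per arm for 0.95 |
|---|---|---|---|
| Difference of log-means, 1.281 | 1.270 | 0.81 / 0.84 / 0.87 / 0.935 | 18 |
| Log ratio of means, 1.399 | 1.387 | 0.87 / 0.90 / 0.92 / 0.967 | 15 |

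**4. Percent change in both arms.** Here d = 30.58 × (fraction of the decline prevented)/SD. The plan gives no SD for the treated arm, so a range is shown. I take ±29.66% to be an SD.

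| Fraction prevented | SD (%) | Power at 12 / 13 / 16 | n per arm for 0.95 |
|---|---|---|---|
| All | 20 | 0.95 / 0.96 / 0.99 | 13 |
| All | 25 | 0.82 / 0.85 / 0.92 | 19 |
| All | 29.66 | 0.68 / 0.71 / 0.81 | 26 |
| All | 35 | 0.53 / 0.57 / 0.67 | 36 |
| All | 20 treated, 29.66 control | 0.81 / 0.84 / 0.91 | – |
| Half | 29.66 | 0.23 / 0.24 / 0.29 | – |

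**5. Post-operative level in both arms.** Assume equal pre-operative levels, no baseline adjustment and the plan's CVs. Complete prevention is then a ratio of 1/(1 − 0.3058) = 1.44; ln 1.44 = 0.365; d = 0.365/0.973 = 0.375; power 0.14 / 0.15 / 0.18 at 12 / 13 / 16. Power 0.95 at 13 per arm needs d = 1.474, a ratio of exp(1.474 × 0.973) = 4.20.

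**6. Table 2 standard errors.** (22.28/6.18)² = 13.0 and (4.31/1.08)² = 15.9. The treatment arm uses 13 and the control arm 16. At 13, the control standard error would be 4.31/√13 = 1.20. This is minor, but the basis is not stated and differs between arms.

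**The case against.** The strongest defence is that the plan intended level against level and simply mislabelled the pilot figure. The sentence about the normal range supports this, as does the log-normal step, and section 3.1 lists AMH measurements as the outcome. With the transformation undone, power at the full 16 per arm is 0.935 to 0.967, close to the claim. The low figures in steps 4 and 5 come from scenarios the plan does not adopt, and the missing Figure 1 prevents a full audit of the transformation. The plan also admits that the pilot is small and calls for an interim analysis.

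Part of this stands. The mislabelling reading is possible, the fall in power under it is moderate, and steps 4 and 5 illustrate size without giving a corrected power. By the exact t method, the fair baseline for the 15 to 18 per arm in step 3 is 12.

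The rest does not rescue the claim. The level reading contradicts the plan's definition of the pilot figure and does not explain why one arm was transformed. Power at 16 per arm ignores the plan's own attrition; at 12 or 13 it is 0.84 to 0.92. Neither the caution about the pilot nor the interim analysis reconciles the two inputs.

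**Conclusion.** The concern holds and needs correcting. As written, 0.95 is not the power for a comparison of the two arms on one outcome.

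No single corrected figure can be given, because the plan does not report the pilot's pre- and post-operative values. The ranges at 12 to 13 evaluable per arm are:

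- **Transformation undone, everything else kept:** 0.84 to 0.92.
- **Percent change, complete prevention of the cited decline:** 0.53 to 0.96 for SDs from 35 down to 20, and 0.68 to 0.71 at 29.66 in both arms.
- **Unadjusted post-operative level, complete prevention:** 0.14 to 0.15.

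The last two assume that the treatment can at best abolish the decline; a rise above the pre-operative level would increase them. They also assume that 30.58% suits the eligible population. The title of reference 19 covers endometriomas as well as other benign cysts, whereas section 4.2 says "This includes cysts defined as dermoid, teratoma, simple cyst, functional, serous cystadenoma or mucinous cystadenoma from the initial diagnostic ultrasound" and does not name endometrioma.

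**What to change.** In section 7.0 and Tables 1 and 2:

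1. Define one quantity on one scale for both arms, for example percent or log-ratio change in AMH from before surgery to 3 months, and state which direction is benefit.
2. Transform both arms' inputs or neither.
3. Confirm that the 30.58% decline applies to the cyst types eligible here before using it.
4. Replace 0.95 with the power at the evaluable number (12 or 13 per arm), as a range with its SD and effect assumptions.
5. State the n behind each standard error in Table 2 and use the same n in both arms.

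The cost is rewriting one section and two tables. Enrolment can stay at 32 with a less favourable stated power. Keeping 0.95 for complete prevention on percent change would instead need 26 evaluable per arm at SD 29.66, or 26/0.75 ≈ 35 enrolled per arm. For SDs of 20 to 35 the range is 13 to 36 evaluable, or 18 to 48 enrolled.
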